3.3. Rationale for choice of target age for cervical screening

This study will target HIV positive and HIV negative women separately. The WHO recommends that: 1) cervical screening should target women 30 years of age and older because of their higher risk of cervical cancer, 2) priority should be given to women aged 30–49 years, and 3) for women of HIV positive status or unknown HIV status in high HIV endemic areas, screening should start as soon as a woman or a girl has tested positive for HIV and is sexually active (WHO screening recommendation update 2014). As the study aims to evaluate the efficacy of screen-and-treat cervical screening algorithms using HPV testing, the start age of HIV positive women to be included in the study will be 25 years of age, to avoid increasing the overtreatment rate as it is known that the prevalence of HPV is higher among young women (less than 30 years) and can be >50% among HIV positive women [23].

WHO recommends age 49 as the upper age limit for screening with VIA. VIA is less effective in women older than 50 years, because the squamocolumnar junction is less visible in postmenopausal women. In this study we want to include women up to the age of 54, in order to compare the performance of HPV testing with or without VIA triage including an age group above 50 years old.

3.4. Cost and Cost-effectiveness methods

3.4.1. Modelling approach

We will use the 'Policy1-Cervix' model platform developed by Cancer Council NSW to model the long-term impact and cost-effectiveness of the interventions. 'Policy1-Cervix' is an extensively validated dynamic model of HPV transmission, HPV vaccination, cervical precancer, cancer survival, screening, diagnosis and treatment. The model has been used for a number of HPV vaccine evaluations, including HPV vaccination in both girls and boys, catch-up vaccination, and the introduction of nonavalent vaccine. The model has also been used to evaluate screening implementation in organized national cervical cancer screening programs in high-income countries and in vaccination and screening in urban and rural areas of middleincome countries. In connection with the Cervical Cancer Elimination Initiative, the model

platform is being used to evaluate the potential impact of screening and HPV vaccination on a global scale.

In the context of this study, the model will incorporate a cervical cancer natural history specific to HIV positive women for application in South Africa. Each country model will be fit to epidemiological data collected from the clinical trial (e.g. age-specific HPV prevalence, HPV type prevalence and distribution, CIN2 prevalence and distribution) and where necessary, supplemental data from countries with similar cervical cancer outcomes and from the literature. Modelled natural history outputs will be validated against expected outcomes from the literature or other relevant sources.

The clinical trial patient pathways (i.e. the screen-and-treat algorithms) for each study arm respective to each study country will be modelled in the platform and country-specific costs collected alongside the trial will be integrated with each intervention. Modelled cost outputs will also be validated against expected values from the literature and relevant sources. Future costs will be estimated by applying official GDP inflators for each country. The patient-navigation component of the CESTA trial will not be included in the modelling.

Other model outputs will include counts of HPV tests, biopsies, laboratory thermoablation treatment, cryotherapy treatment, CIN2 detected and colposcopies.

3.4.2. Costs

The assessment of costs will be conducted from the health service provision and the patient perspective.

_	Costs included	Estimation method	Data sources
Provider	Direct medical costs of cervical cancer screening and treatment and follow-up (HPV test, VIA, biopsy, lab fees, thermoablation, cryotherapy, colposcopy, clinical staff, medical supplies).	Ingredient approach	Observation, records, primary data collection
	Other recurrent and capital costs (overhead costs such as building, utilities), programme costs (e.g. costs of community recruitment in Senegal).	Step-down costing for overhead costs; ingredient approach for other	Health facility records and primary data collection
Patient/client	Direct medical (e.g. ancillary drugs) and non-medical costs (food and round-trip transportation)	-	Questionnaire
	Indirect costs (time costs)	Human capital method	Questionnaire

Table 1. Overview of costs and data collection methods

Health services costs: Direct medical costs on screening, diagnosis and treatment of precancerous lesions will be calculated using a micro-costing approach whereby quantities of resources used will be measured and multiplied by their respective unit cost or price. These will include the costs of staff (time and by type), consumables, equipment, quality assurance and control (for VIA) and transportation of cervical samples. We will use the micro-costing approach to estimate the cost of (i) HPV DNA testing, (ii) VIA testing, (iii) colposcopy, (iv) biopsy and (v) pre-cancer treatment (thermocoagulation and cryotherapy). Aggregate health facility expenditures (e.g. utilities) and capital costs (e.g. building, equipment and furniture) will be allocated to the different interventions provided using a step-down costing approach. Step-down costing will only be performed if required (e.g. if new facilities are set up). In addition to these costs, we will also consider programmatic costs. In South Africa this will include the cost of setting up recruitment at ART clinics and diversion to the appropriate clinical site. In the case of Senegal where recruitment will take place in the community, this will include the costs of information, education and communication (IEC) materials (e.g. advertisements on the radio, community sensitization activities), staff training, monitoring and evaluation and supervision.

Woman's costs: For the patient perspective, we will collect data on direct medical, nonmedical and indirect costs. Direct non-medical costs include the cost of transportation to and from home or work to the different health facilities and food. Indirect costs consist of time losses resulting from travelling to and from the health facilities, waiting and receiving care. These time losses will be valued with the human capital method using income data collected from women and/or published wage rates.

3.4.3. Data collection

Health services costs: Data on direct medical costs will be collected in association with 10% of the study participants. All costs incurred for the various interventions will be identified through observation of processes, time sheets where available and extensive consultation with the medical, laboratory and programmatic staff. Observations will include time-and-motion measurement of the various staff procedures and will be done by trained research staff. Data on overheads will be obtained from the health facilities directly.

Women's costs: To measure the costs incurred by study participants, repeated measurements on non-medical costs and travelling and waiting time will be carried out at each visit of the study participant to the health facility. Data will be collected through the administration of questionnaires by the research staff at each visit to the clinical sites. More in depth data to probe and validate time costs will be collected through convenience sampling of 10% of the participants using in-person interviews. During the first visit, the questionnaire will also include information on socio-demographic characteristics and income.

3.4.4. Effectiveness and cost-effectiveness evaluation

For each screening arm, we will calculate the predicted average lifetime reduction in the agestandardised rate of cervical cancer incidence and mortality, as well as the number of deaths averted and histologically confirmed high grade lesions.

In terms of cost-effectiveness, we will use a limited societal perspective with a lifetime time horizon and 3% discounting. The relative performance of the different screening strategies will be expressed in terms of the incremental cost-effectiveness ratio, representing the additional cost of a strategy divided by its additional benefit, compared to the next least expensive alternative and expressed as cost per quality-adjusted life year (QALY) and cost per life-years saved. Other outcomes include cost per CIN2 detected and cost per treatment

performed. We will also estimate the annual budget impact of the different interventions and annual resource utilisation in terms of number of colposcopies, biopsies, precancer treatments, HPV tests, triage tests and other relevant procedures when considering scaling-up of the interventions.

3.5. Statistical methods Module 1 Algorithms study

For main objective 1, we will use three different indicators: 1) percentage of HPV positive women with detected histological HSIL+ treated in each arm, 2) percentage of HPV positive women without histological HSIL+ lesions treated in each arm, and, 3) percentage of HPV positive women that are referred to colposcopy by VIA in arm 1 or VAT in arm 2. Proportions in each arm will be compared using Chi-square likelihood ratio tests. In addition, 95% confidence intervals will be estimated for each proportion and used graphically for comparison.

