HIV positive women will be recruited from HIV care clinics, also called antiretrovirals (ARV) clinics in the Durban area, South Africa. After giving informed consent, women will be screened with HPV testing and those that are HPV positive will be randomized at a 4:1 ratio into HPV + VIA + treat (Arm 1) and HPV + treat (Arm 2) in 1 of the 2 CESTA study clinics. Women in Arm 1 will receive VIA and only positive for VIA will be treated. In Arm 2, all HPV positive women will be treated. Women that are eligible for ablative treatment will be randomized into treatment with TA or cryotherapy in both arms. Others will be referred to colposcopy. After VIA in Arm 1 or before treatment in Arm 2, the nurses will collect 2-4 biopsies on all HPV positive women. The biopsies will be used as gold standard for disease detection. The first 200 women treated will be followed up intensely for 4 weeks to assess side-effects and levels of HIV shedding. Subsequently treated women will be called by telephone after 1 week and 1 month to assess side-effects and satisfaction with the procedures. Smartphone enhanced VIA (SEVIA) with patient navigation will be used in 1 of the 2 study clinics. 2-3 Pictures are taken with the SEVIA smartphone tool after application of acetic acid to the cervix. The pictures are sent in a secure way to expert reviewers who provide feed-back to the nurse in real time. The application can also be used to track adherence of the

women to the screen and treat procedures or referral and send automated reminders of appointments. Outcomes on performance of VIA and patient adherence will be compared between study clinic that uses SEVIA and the one not using SEVIA. All women who were HPVpositive or were treated will be called back after 1 year for a follow-up visit. Women will be screened with HPV testing and VIA and 2-4 colposcopy-directed biopsies will be taken from all HPV positive women. Women with remaining/recurrent CIN2+ disease will receive appropriate management.

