The CESTA study aims at comparing two algorithms for screening and treatment of high-grade cervical pre-cancer lesions in populations of HIV positive and HIV negative women; in addition the study aims to compare the efficacy (cure rate) of cryotherapy and thermal ablation in HIV positive women. The CESTA study is therefore comprised of 2 modules.

Module 1 is a randomised controlled trial of 2 screen and treat algorithms: screening women with HPV test followed by triage with VIA and treatment versus screening women with HPV test without VIA triage and followed by treatment in HIV positive women (in South Africa, women 25 – 54 years) and among HIV negative women (in Senegal, women 30 – 54 years).

Module 2 is a randomised controlled trial to compare the cure rates of thermal ablation versus cryotherapy in HIV positive women aged 25-54 years with CIN2/3; module 2 will also be carried out in South Africa.

3.1. CESTA Module 1: Randomised control trial of two algorithms, screening with HPV tests followed by VIA as a triage and treatment (HPV + VIA + treat), vs screening with HPV test followed by treatment (HPV + treat) among HIV-positive women in South Africa and HIVnegative women in Senegal

3.1.1. Primary Objectives:

- To compare the efficacy of HPV + VIA + treat and of HPV + treat cervical cancer screening algorithms by comparing the proportion of women with histological HSIL that receive treatment or not through each algorithm in HIV positive and HIV negative women.
- To model the cost-effectiveness of the HPV + VIA + treat and HPV + treat strategies, in HIV negative and HIV positive populations.

3.1.2. Secondary Objectives:

- 1. To assess the proportion of overtreatments (in women with no lesions or CIN1) that was avoided by VIA triage.
- To assess the VIA performance in clinics using Smartphone Enhanced VIA (SEVIA) compared to clinics that don't.
- To assess patient adherence to study visits in clinics using SEVIA compared to clinics that don't.
- 4. To assess the performance of VIA as a test of cure 1 year after treatment.

- 5. To estimate the HPV infection clearance rate after one year of the treatment.
- 6. To describe the safety and side effects of cryotherapy and thermal ablation.
- 7. To assess and compare the HIV shedding among women treated with cryotherapy and thermal ablation.
- 8. To measure the HPV results agreement between self-collected and clinician-collected samples in HIV positive women.

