Women with CIN2+ on biopsy who have not been treated based on screening results from arm 1 will also be randomised to sub-arms A and B if eligible for ablative treatment or referred to colposcopy otherwise.

ARM 2:

Study procedures in this arm are mostly similar to Arm 1. A nurse will carry out a speculum examination and collect an endocervical swab to measure HIV shedding. She will then perform a visual assessment for treatment using acetic acid (VAT, see section 2.4) to assess if the patient is eligible for ablative treatment and in half of the study clinics, 2-3 pictures will be taken with the SEVIA App. After VAT, 2-4 biopsies will be collected at the SCJ from all quadrants that show aceto-white changes or at 12 and 6 'o clock if no acetowhite changes are visible.

All women that are eligible for ablative treatment will be treated and randomised into subarm A (cryotherapy) and sub-arm B (thermal ablation) as in Arm 1; women with VAT not eligible for ablative treatment will be referred to the colposcopy clinic for appropriate referral and management.

Similar as for VIA, the VAT examination is inadequate if the SCJ is not entirely visible. In this case, an endocervical brush will be collected for cytological examination and the woman will be referred to colposcopy once the cytology result is known.

In both arms, endocervical sample collection for HIV shedding will be done after 1, 2, 3, and 4 weeks in 100 women (each arm) who received treatment (modes of selection for these women still needs to be decided). At those respective visits, women will answer a questionnaire on perceived side-effects and acceptability of treatment. Women who do not come back for HIV shedding sample collection will be called by telephone after 1 week and 1 month to assess perceived side-effects and acceptability of treatment. The nurse will take the necessary actions if serious side-effects are reported.

In addition, all treated women will be recalled at 12 months for a follow-up visit including HPV testing, VIA with colposcopy and biopsy on HPV positive women, and those with CIN2+ will be treated as appropriate.

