Women with CIN2+ on biopsy who have not been treated based on screening results from arm 1 will also be recalled and treated with TA eligible for ablative treatment or referred to colposcopy otherwise.

ARM 2:

Study procedures in this arm are mostly similar to Arm 2 among HIV positive women (section 3.2.1). A nurse will carry out a speculum examination and perform a VAT to assess if the patient is eligible for ablative treatment and in half of the study clinics, 2-3 pictures will be taken with the SEVIA App. After VAT, 2-4 biopsies will be collected at the SCJ from all quadrants that show aceto-white changes or at 12 and 6 o'clock if no acetowhite changes are visible.

All women that are eligible for ablative treatment will be treated by TA; women with VAT not eligible for ablative treatment will be referred to the colposcopy clinic for appropriate referral and management.

VAT examination is inadequate if the SCJ is not entirely visible. In this case, an endocervical brush will be collected for cytological examination and the woman will be referred to colposcopy once the cytology result is known.

In both arms, women who receive treatment will be called by telephone after 1 and 4 weeks and a questionnaire on perceived side-effects and acceptability of treatment will be taken by the nurse. The nurse will take the necessary actions if serious side-effects are reported. In addition, all treated women will be recalled at 12 months for a follow-up visit including HPV testing, VIA, colposcopy and biopsy on HPV positives, and those with CIN2+ will be treated as appropriate.

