3.5.1. Sample size and power calculations

For the first objective, to compare the performance of the algorithms, the sample size has been calculated for the three indicators defined above. We used the percentage of HPV positive women with HSIL+ who were treated for the sample size calculation as it is the indicator that requires the largest sample size.

For HIV positive women, we assumed several features as follows: HPV testing sensitivity of 95%, 85% eligibility for ablative treatment and an overall attrition of 20% for both arms. Additionally, for Arm 1 (HPV+VIA), we assumed a VIA sensitivity among HPV positive women of 75% and 4% VIA result of suspected cancer or VIA inadequate. Using a randomisation ratio of 4:1 to Arm 1 and Arm 2, we will need to detect 125 histological HSIL+ cases in Arm 1 and 25 histological HSIL+ cases in Arm 2.

With 3000 HIV positive women attending screening, assuming 50% HPV positivity [24-26] and 50% VIA positivity, and a prevalence of 5% HSIL we will have at least 85% power to detect a difference of 24% (72.8% in Arm 1 vs 97% in Arm 2) with two-sided type error I 0.05 (see Table 2 and Table 3). In summary, under all assumptions stated, 1500 HPV positive women will need to be included.

Outcomes	Total	Arm VIA (1)	Arm HPV (2)	Difference
Total HSIL+ cases (n)	150	120	30	
Total HSIL+ HPV positive cases (n)	143	114	29	
Total HSIL+ treated (n)	111	83	28	
Total <hsil treated
(overtreatment) (n)</hsil>	742	487	254	
% of treatment among HSIL+ HPV positive women		72.8%	97.0%	24%
% of overtreatment among HPV positive women		41%	85%	44%

Table 2. Differences expected according to number of histological HSIL+ cases treated and<HSIL women overtreated in HIV positive women	Table 3. Number of HIV positive women to be screened

Sample size	Parameter	n arm VIA (1)	n arm HPV (2)
Prevalence of HSIL+	0.05		
Expected number of HIV positive women (n)	3000	2400	600
Power	>85%		

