Similarly for HIV negative women, randomising in a 3:1 ratio to Arm 1 or Arm 2, under the same assumptions for sensitivities (HPV 95%, HPV, VIA 75% in HPV positives, 85% eligibility for ablative treatment in Arms 1 and 2, and 20% attrition overall), we will need to detect 113 HSIL+ cases in Arm 1 and 38 in Arm 2 to compare the percentage of women with HSIL+ treated under each algorithm. With a sample size of 7500 HIV negative women, assuming 15% HPV prevalence [27], 50% VIA positivity, 2% prevalence of HSIL+, and two-sided type error I of 0.05, we will have at least 85% power to detect a difference of 24% (72.8% in Arm 1 and 97% in Arm 2) in the percentage of HPV positive women with HSIL+ treated (see Table 4 and Table 5). In summary, under all the assumptions stated, 1125 HIV negative HPV positive women will need to be included.

Outcomes	Total	Arm VIA (1)	Arm HPV (2)	Difference
Total HSIL+ cases (n)	150	113	38	
Total HSIL+ HPV positive cases (n)	143	107	36	
Total HSIL+ treated (n)	112	78	35	
Total <hsil treated
(overtreatment) (n)</hsil>	553	323	230	
% of treatment among HSIL+ HPV positive women		72.8%	97.0%	24%
% of overtreatment among HPV positive women		38%	82%	43%

Table 4. Differences expected according to number of HSIL+ cases treated and <HSIL women	overtreated in HIV negative women

Table 5. Number of HIV negative women to be screened and randomized

Sample size	Parameter	Arm VIA (1)	Arm HPV (2)
Prevalence of HSIL+	0.02		
Expected number of HIV negative women (n)	7500	5625	1875
Power	>85%		

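### Could indicator 1 of Module 1 count Arm 1 women who were treated only because of the study biopsy?

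*Protocol*

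**What the plan says.** Protocol Section 3.5 introduces three indicators for main objective 1. The first is the "percentage of HPV positive women with detected histological HSIL+ treated in each arm". The second is the matching percentage for women without HSIL+. The third does name its trigger: "percentage of HPV positive women that are referred to colposcopy by VIA in arm 1 or VAT in arm 2". Section 3.5.1 sizes Module 1 on the first.

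Every HPV positive woman is biopsied, and the Executive Summary gives the purpose: "The biopsies will be used as gold standard for disease detection". The biopsy also leads to care:

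- Section 3.2.1 (South Africa, Arm 1): "Women with CIN2+ on biopsy who have not been treated based on screening results from arm 1 will also be randomised to sub-arms" (cryotherapy or thermal ablation), or referred to colposcopy.
- Section 3.2.2 (Senegal, Arm 1): "Women with CIN2+ on biopsy who have not been treated based on screening results from arm 1 will also be recalled and treated with TA", or referred to colposcopy.

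No matching rule is written for Arm 2.

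The primary objective (Section 3.1.1) compares the "proportion of women with histological HSIL that receive treatment or not through each algorithm". The HIV negative part of Section 3.5.1 gives the purpose of the case numbers as "to compare the percentage of women with HSIL+ treated under each algorithm". Tables 2 and 4 put indicator 1 at 72.8% in Arm 1 and 97.0% in Arm 2.

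**The concern.** The biopsy is the study's reference standard and is not a step of the HPV + VIA + treat algorithm. By Section 2.7, histological HSIL is p16-positive CIN2, CIN3 or adenocarcinoma in situ, so an HSIL woman whom VIA calls negative falls under the recall rule. If treated in Arm 1 meant treated for any reason, these women would count as successes of an algorithm that missed them. The more completely the study recalled them, the more VIA triage would look like immediate treatment. This would mask what Section 2.3 worries about, namely that VIA's limited sensitivity could undermine the combined strategy.

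The wording invites the question because indicator 3 names its trigger and indicator 1 does not. Indicator 2 is equally open. Treatment follows a CIN2 cut-off while the outcome is HSIL+, so a recalled woman with p16-negative CIN2 could be counted as overtreated although the algorithm did not treat her.

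**Working it through.** **Inputs (Section 3.5.1, Tables 2 and 4).** VIA sensitivity in HPV positive women 75%; eligibility for ablation 85%; attrition 20%; HSIL+ HPV positive cases 114 and 29 (South Africa), 107 and 36 (Senegal); likelihood-ratio chi-square test, two-sided 0.05. Recall uptake *r* is not in the documents and is an assumption here.

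**Step 1: the plan's own figures.** The protocol does not write out how it reached 97.0% and 72.8%. The following build-up is inferred and reproduces both:

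- Arm 2: 0.85 + 0.15 × 0.80 = 0.970
- Arm 1: 0.75 × 0.970 = 0.7275

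Table 2 has 83/114 = 72.8% in Arm 1, and Table 4 has 78/107 = 72.9%. The 25% of HSIL+ women missed by VIA (0.25 × 114 = 28.5; 0.25 × 107 = 26.75) add nothing to the Arm 1 numerator. The planners therefore counted them as untreated.

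A continuity-corrected two-proportion calculation at 85% power, 72.8% against 97% and 4:1 allocation gives 120 and 30 cases, exactly the first row of Table 2.

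**Step 2: power on the intended reading.** Exact enumeration of the likelihood-ratio test at 0.7275 against 0.97 gives 95.7% for 114 against 29 and 98.0% for 107 against 36. The pooled Z approximation gives 91.8% and 95.7%. All exceed the stated 85%.

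**Step 3: what the other reading would do.** If recalled VIA-missed women counted as treated, with the same 97% completion:

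Arm 1 = 0.75 × 0.97 + 0.25 × *r* × 0.97

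| *r* (assumed) | Arm 1 | Difference from 97.0% | Exact power, 114 vs 29 | Exact power, 107 vs 36 |
|---|---|---|---|---|
| 0 | 72.75% | 24.25 points | 95.7% | 98.0% |
| 50% | 84.9% | 12.1 points | 58.7% | 65.5% |
| 80% | 92.2% | 4.85 points | 22.6% | 26.4% |
| 100% | 97.0% | 0 | 2.9% | 4.4% |

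At *r* = 80% this moves 28.5 × 0.8 × 0.97 = 22.1 women in South Africa (83 becomes about 105 of 114) and 26.75 × 0.8 × 0.97 = 20.8 in Senegal (78 becomes about 99 of 107).

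The recall rule covers all untreated Arm 1 women with CIN2+, including VIA positive women who did not complete treatment. Applied to the whole untreated 27.25%, full uptake would give 0.7275 + 0.2725 = 100% against 97%, a difference in the opposite direction. The other reading would therefore not err only towards no difference.

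**Step 4: which reading the protocol supports.**

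- The sentence in Section 3.5 opens by tying its indicators to main objective 1, and Section 3.1.1 words that objective as treatment received through the algorithm.
- The last part of Section 2.1 sets HSIL+ women who were treated against those who remained without treatment. The second group would lose most of its meaning in Arm 1 if recalled women moved out of it.
- Section 3.5.1 speaks of comparing how the algorithms perform and of women treated under each one.
- The recall rules in Sections 3.2.1 and 3.2.2 themselves separate these women from those treated on the screening result.
- Tables 2 and 4 work the indicator through with no term for recalled women.

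Nothing in the protocol says that biopsy-triggered treatment counts for the algorithm.

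**The case for a change.** The strongest case for a change is that Section 3.5 is the operative definition. Section 3.5.1 refers back to it, an analyst works from it, and it is looser than both the objective and indicator 3. In South Africa, women treated after the biopsy also enter the same sub-arms A and B as women treated on VIA, so a simple treated flag would mix the two groups. The remedy would be one sentence and one data field.

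Part of this stands. The wording is looser than it should be, and repeating the restriction in Section 3.5 would help a reader who sees only that section. But the sentence does not conflict with the objective; it refers to it.

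The two groups can also largely be separated without a new field. VIA performance is a secondary objective, so the VIA result has to be available, and in Arm 1 a VIA negative woman is not treated by the algorithm at all. The trigger is less obvious for VIA positive women who did not complete treatment at first. On the planning values they are 0.75 × 0.03 = 2.25% of HSIL+ women, or 0.0225 × 114 = 2.6 in South Africa and 0.0225 × 107 = 2.4 in Senegal.

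Which treatment event enters a numerator, and how its trigger is recorded, is commonly settled in the SAP, which was not available for this review. A clarifying sentence would also need care. Copying indicator 3 and tying Arm 2 treatment to VAT would misdescribe that arm, where HPV positivity leads to treatment and VAT only checks eligibility for ablation (Section 2.4).

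The indicator 2 point is real in principle, but the documents give no figure for p16-negative CIN2, so its size cannot be stated.

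**Conclusion.** No change to the plan follows. Section 3.5 leaves out a restriction that the objective, the sample-size text, the recall rules and the planning tables all carry. An analyst who follows the whole protocol would leave treatment triggered only by the study biopsy out of indicators 1 and 2. On that reading the planned contrast of 72.8% against 97% is unchanged, and exact power is 95.7% and 98.0% against a stated minimum of 85%. This rests on the inferred build-up 0.75 × (0.85 + 0.15 × 0.80), which reproduces both planning percentages.

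The smaller contrasts of 12.1, 4.85 or 0 points need two things together: a reading that the protocol contradicts, and a recall uptake (50%, 80% or 100%) that it does not give. They show what is at stake if the indicator were misapplied; they do not show an error in the plan. Spelling out the restriction when the endpoint is defined for analysis would be a reasonable clarification, and it would alter neither the design nor the sample size.
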